The open-label, single group phase I study trial (1368.11) was conducted to investigate the safety, tolerability, pharmacokinetics, pharmacogenomics, and efficacy of a single intravenous dose of BI 655130 (10 mg/kg) in 7 patients with acute flare of generalized pustular psoriasis. Based on the PK results in GPP patients, the elimination half-life of BI 655130 was approximately 3 weeks in GPP patients. The proof-of-concept (PoC) for IL36R inhibition in GPP was achieved in these patients who showed rapid clinical responses to single administrations of BI 655130. Five of these 7 patients became clear or almost clear of GPP 1 week after the infusion, and all of them reached this status by 4 weeks after treatment. Within 48 hours of treatment, pustules were completely cleared in 3 patients; pustules were cleared by Week 1 in 5 patients, and by Week 2 in 6 patients. The early response in the skin was also accompanied by an early response in systemic components (C-Reactive Protein [CRP] approaching normalization within 4 weeks). A major improvement in GPPASI was observed in all patients very early with a mean (SD) percent change from baseline of 73.2% (16.2) at Week 2; by Week 4, this was further reduced to 79.8% (15.6), and was maintained to Week 20 (83.6%). Additional improvements (mean [SD]) from baseline to Week 2 were observed in FACIT-F, 12.3 (10.1); Pain-VAS, -45.9 (32.3); and PSS, -5.14 (3.18), all of which were also sustained through Week 4. For further details and most recent results refer to

the current IB ([c03320877](#)) and published letter in the New England Journal of Medicine ([P19-01888](#)).

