Patients will be offered to enter into an open label extension (OLE) trial (1368-0025), if they have completed the treatment period in this study up to EoS1 (i.e. without premature discontinuation of trial treatment), agree to participate in the OLE trial and meet the eligibility criteria for the OLE trial.

Patients who do not qualify to enter into the open label extension (OLE) trial or who may have qualified, but do not agree to participate in the OLE trial, will be followed as described in [section 3.3.4.1](#) handling of patients with premature treatment discontinuation.

The primary analysis of this trial is planned to be performed once all randomized patients have completed or early discontinued from the 48 week treatment period; a database lock for the primary analysis will then be performed. Final analysis is planned to be performed at the end of the trial once all randomized patients have completed the trial (including any follow-up period) if applicable.

The primary analysis and final analysis may be performed as a single analysis (at the time of trial completion), if, prior to the time of the primary analysis, the trial team agrees that the expected time interval between the planned analyses is insufficient to justify the performance of separate analyses.

Handling of GPP Flares:

If a patient experiences the first GPP flare (increase in GPPGA score by ≥ 2 from baseline and the pustular component of GPPGA ≥ 2) during the randomized maintenance treatment period, a rescue treatment with i.v. open label dose of 900 mg BI 655130 should be administered (R1/D1). The investigators should encourage the patient to inform them at the first signs of onset of a GPP flare. If a patient suspects that they have a GPP flare in between the protocol specified scheduled visits, they should contact the investigator to determine whether to make an unscheduled visit and return to the clinic/site for assessment. After confirming the onset of a GPP flare requiring treatment and subsequently receiving the i.v. dose of BI 655130, the patients will be seen at R2/D4 and R3/D8 of week 1 (daily if hospitalized), week 2, week 3, week 4, and week 8 of the rescue treatment period (see [Flow Chart 2](#)). A patient may qualify to receive another rescue treatment with open label i.v. dose of 900 mg of BI 655130 at R3/D8, if either of the following criteria are met.

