- **For patients with GPPGA score of ≥ 3 and a pustular component of GPPGA of ≥ 2 at R1:** the total GPPGA is ≥ 2 and the pustular component of GPPGA is ≥ 2 at R3/D8.
- **For patients with GPPGA score of 2 and a pustular component of GPPGA of ≥ 2 at R1:** the pustular component of GPPGA is ≥ 2 at R3/D8.

For patients who receive the administration of the first rescue treatment with open label i.v. (OL) BI 655130 for the first GPP flare up to Week 34 (Day 239) of randomization, after 12 weeks following the day of rescue i.v. treatment administration (R1 in Flow Chart 2) and response of the GPP flare, they will start the OL s.c. maintenance treatment period to receive the OL s.c. dose of 300 mg BI 655130 q12w. The visits of BI 655130 q12w during the OL s.c. maintenance treatment period should follow [Flow Chart 1](#). Therefore, the visit of the first s.c. OL maintenance treatment should be assigned to a planned visit per Flow Chart 1 by comparing to the day of the first randomized treatment (V2/D1 in Flow Chart 1). If the first dose of OL s.c. maintenance treatment is outside of any scheduled visit window by ± 7 days per Flow Chart 1, it needs to be assigned to one of the scheduled visits by extending each visit time window to -13/+14 days of the original CTP planned visit date, defined relative to

the day of first randomized treatment, Day 1. See [Table 3.1: 1](#) for the detailed rules of visit assignment for the first dose of OL s.c. maintenance treatment. Then the following OL s.c. maintenance doses (if applicable) will be administered within original visit window by ± 7 days per [Flow Chart 1](#). Note that once the first dose of OL s.c. visit assignment referring to Flow Chart 1 is calculated (see Table 3.1:1), all study procedures scheduled for this visit and subsequent OL maintenance treatment visits should be completed as per open label maintenance treatment period in [Flow Chart 2](#).

During the maintenance treatment with OL s.c. dose of 300 mg BI 655130 q12 weeks, if the patient's GPPGA total score increases by ≥ 1 (with or without the presence or new appearance of pustules), or if there is an increase in the pustular component of GPPGA ≥ 1 from any of the previous OL maintenance visit(s), then the investigator may treat the patient with intensified maintenance therapy with open label s.c. dose of 300 mg BI 655130 q4 weeks.

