4.1.2 Selection of doses in the trial and dose modifications

In the proof-of-concept trial 1368.11 in GPP patients, a single intravenous dose of 10 mg/kg of BI 655130 was tested. The proof-of-concept (PoC) for IL36R inhibition in GPP was achieved in these patients who showed rapid clinical responses (for further detail, refer to [Section 1.2](#)). GPPASI score was measured at weeks 1, 4, 12 and 20 and the positive response was maintained up to week 20 following this single i.v. dose of BI 655130. Additionally, a 300 mg s.c dose of BI 655130 has been tested in healthy volunteers to obtain PK information following sub-cutaneous administration of BI 655130.

The aim of the current trial (1368-0027) is to provide dose-ranging data for 3 subcutaneous dosing regimens of BI 655130 with the proposed doses of 300 mg s.c. q4w and 300 mg s.c. q12w after a loading dose of 600 mg each and 150 mg q12w after a loading dose of 300 mg. These three doses/regimen were selected to test a wide range in exposure to thoroughly evaluate the exposure-response relationship of BI 655130 in GPP patients.

If a patient experiences a GPP flare (increase in GPPGA score by ≥ 2 from baseline and the pustular component of GPPGA ≥ 2) during the randomized maintenance treatment period, a rescue treatment with i.v. open label dose of 900 mg BI 655130 is to be administered at R1/D1. A patient may qualify to receive another dose of i.v. open label 900 mg BI 655130 at R3/D8 if protocol specified criteria are met (please refer to [Table 3.1:1](#)). The 900 mg BI 655130 i.v dose was selected based on positive data from 1368.11 and thus considered reasonable to continue with the dose of 10 mg/kg to maintain the PK exposures observed in the trial 1368.11. A fixed dose of 900 mg was selected to give the flexibility to recruit patients greater than 70 kg body weight. BI 655130 has been tested in healthy volunteers up to 20 mg/kg (given weekly in the MRD trial 1368.2) and was shown to be safe and tolerable. Evaluation of the PK data in GPP patients suggest that BI 655130 exposure in patients was lower when compared to PK in healthy volunteers (HVs). Thus, the selected fixed dose (900 mg single i.v. dose) is anticipated to be within safety limits for patients with a lower weight as well.

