Including adolescent patients with a minimum weight of 40 kg is not expected to pose any safety concern as the predicted exposures in adolescents with the doses planned are expected to be below the maximum exposures tested in healthy volunteer trials. Using the population PK model built from healthy volunteers and PK data from PPP patients, one thousand simulations were performed for a typical 40 kg subject taking into account inter-individual variability in model parameters.

Forty kilograms was chosen for the simulations as this represents the weight of the lightest subject that could be enrolled in this trial. Assuming the subjects receive the highest maintenance dose of 300 mg q4w until week 32 and then receives a 900 mg IV rescue dose at week 33 (worst case scenario for exposure, where the IV dose is administered 1 week after the last s.c. dose representing administration at t_{max}), the predicted median C_{max} following rescue dosing is 487,000 $\mu\text{g/L}$ (314,000 – 756,000 $\mu\text{g/L}$ (90% prediction interval)). This is well below the maximum observed concentration of 992,000 $\mu\text{g/L}$ following the maximum tested dose of 20 mg/kg qw (x4 doses) in trial 1368.2.

Similarly, the model predicted median AUC over 12 weeks following rescue dosing is 9,620,000 $\mu\text{g/L} \cdot \text{day}$ (6,320,000 – 14,100,000 $\mu\text{g/L} \cdot \text{day}$ (90% prediction interval)) which is well below the model predicted AUC over 12 weeks of 31,900,000 $\mu\text{g/L} \cdot \text{day}$ (26,300,000 – 38,700,000 $\mu\text{g/L} \cdot \text{day}$ (90% prediction interval)) following the maximum tested dose of 20 mg/kg qw (x4 doses) in trial 1368.2.

The weight cutoff was chosen as 40 kg (median weight of a 12 year old subject) and not 30 kg (3rd percentile for a 12 year old subject) because the probability of exceeding the maximum observed concentration was calculated as 0.5% for subjects weighing 40 kg while the probability of exceeding the maximum observed concentration was 4.4% for subjects weighing 30 kg.

The expected exposure profile is shown in [Figure 4.1.2:1](#). The blue line and shaded area represents the median and 90% prediction interval following 300 mg q4w maintenance dosing and then administration of a rescue dose at week 33 for a typical 40 kg adolescent, taking into account inter-individual variability in model parameters. The black line and shaded area represents the median and 90% prediction interval for the same scenario in

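### The exposure case for the 40 kg minimum weight is built on one 900 mg rescue infusion, but the protocol allows a second one seven days later

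*Protocol*

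**What the plan says.** Section 4.1.2 of the protocol reports 1,000 simulations of a typical 40 kg subject on the highest maintenance regimen, with rescue given as "900 mg IV rescue dose at week 33 (worst case scenario for exposure, where the IV dose is administered 1 week after the last" maintenance injection. The predicted median Cmax is 487,000 ug/L (90% prediction interval 314,000 to 756,000) and the median 12-week AUC is 9,620,000 ug/L·day. The comparators come from 20 mg/kg weekly for four doses in trial 1368.2: a maximum observed concentration of 992,000 ug/L and a model-predicted AUC of 31,900,000 ug/L·day.

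Two conclusions follow in that section. For adolescents, "the predicted exposures in adolescents with the doses planned are expected to be below the maximum exposures tested in healthy volunteer trials". For the weight limit, "the probability of exceeding the maximum observed concentration was calculated as 0.5% for subjects weighing 40 kg", against 4.4% at 30 kg, and this comparison is the stated reason for choosing 40 kg.

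The same section also says: "A patient may qualify to receive another dose of i.v. open label 900 mg BI 655130 at R3/D8 if protocol specified criteria are met". Section 3.1 repeats the permission ("A patient may qualify to receive another rescue treatment with open label i.v. dose of 900 mg of BI 655130 at R3/D8"). For a patient with GPPGA of at least 3 at R1, the condition is that "the total GPPGA is ≥ 2 and the pustular component of GPPGA is ≥ 2 at R3/D8"; for a patient with GPPGA of 2 at R1, only the pustular score counts. Weight, age and randomized arm play no part. Tables 4.1.1: 1 and 4.1.4: 1 list rescue at R1/D1 alone or at both R1/D1 and R3/D8.

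**The concern.** The scenario labelled as the worst case is not the highest exposure the protocol allows. A 40 kg patient who qualifies at R3/D8 receives 1,800 mg within eight days (1,800/40 = 45 mg/kg), whereas the simulation gives 900 mg (22.5 mg/kg). With a half-life of three to four weeks, much of the first infusion is still present when the second is given, so the second peak must be higher than the first.

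Two details suggest that the section was not updated for the second infusion. It still rests its reassurance for lighter patients on one infusion: "the selected fixed dose (900 mg single i.v. dose) is anticipated to be within safety limits". It also sends the reader to Table 3.1: 1, which holds visit windows, for the R3/D8 criteria, which are in Table 3.1: 3. That pointer is only clerical.

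What is at stake is the margin shown to investigators and ethics committees who are deciding on adolescents and light adults. The 0.5% stands behind an eligibility threshold, and it does not cover the regimen that the threshold admits patients to.

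**Working it through.** Concentrations are in mg/L (1 mg/L = 1,000 ug/L).

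**1. Reproduce the stated 0.5%.** Take Cmax as log-normal with the Section 4.1.2 median and interval.
- log-SD = ln(756/487)/1.645 = 0.267. The lower half of the interval gives the same value.
- P(Cmax > 992) = 1 − Φ[ln(992/487)/0.267] = 0.0039.

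That is about 4 in 1,000 simulations, against 5 in 1,000 stated. The 0.5% is therefore a one-infusion figure.

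**2. Fit a model to the protocol's figures.**
- Dosing: 600 mg s.c. on day 0, 300 mg s.c. every 28 days to day 224, 900 mg i.v. over 90 minutes on day 231.
- From the protocol: s.c. bioavailability about 70% and half-life 3 to 4 weeks (Section 1.2); Cmax 487 and 84-day AUC 9,620 (Section 4.1.2).
- Assumed, not in the documents: linear two-compartment kinetics, inter-compartmental clearance 0.1 to 0.8 L/day, s.c. absorption rate 0.15 to 0.4 per day, and the same log-SD after the second infusion.

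Clearance and the two volumes were solved so that Cmax, AUC and half-life (21, 24.5 or 28 days) match exactly. Five clearance values and three absorption rates give 3 × 5 × 3 = 45 fits, all exact.

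**3. Add a second 900 mg on day 238.** One fit as an example (half-life 24.5 days, inter-compartmental clearance 0.4, absorption rate 0.25):
- The s.c. level before the first infusion is 79, so one infusion adds 487 − 79 = 408.
- On D8, 50% of the first peak remains: 0.50 × 487 = 244.
- Second peak ≈ 244 + 408 = 652 (model: 651).
- P(> 992) = 1 − Φ[ln(992/651)/0.267] = 5.8%.

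Results over the 45 fits:

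| Quantity | One infusion (stated) | Two infusions |
|---|---|---|
| Median Cmax | 487 | 631 to 706 |
| P(> 992) | 0.5% | 4.5% to 10.2% (median fit 6.9%) |
| Median 12-week AUC | 9,620 | 16,154 to 16,889 |

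**4. Check with between-patient variability.** Four Monte Carlo runs of 1,500 patients, tuned to the stated 90% intervals, gave 0.47% to 0.53% for one infusion and 4.9% to 6.6% for two.

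**5. Wider assumptions.** Write the second peak as 487 × (r + f), where r is the share of the first peak left at day 7 and f the share due to the infusion. With r from 0.6 to 0.85 and f from 0.5 to 0.8, the median peak is 536 to 804 and the exceedance about 1% to 22%.

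**6. Weight for the chance of qualifying.** In trial 1368.11, "pustules were cleared by Week 1 in 5 patients, and by Week 2 in 6 patients", of seven treated, so at most 2 of 7 could have met the pustular criterion at day 8.
- Low: (2/7)(0.045) + (5/7)(0.0039) = 1.6%.
- High: (2/7)(0.102) + (5/7)(0.0039) = 3.2%.

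With the exact 95% interval for 2/7 (0.037 to 0.71), the median fit gives 0.6% to 5.0%.

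**7. Compare with 30 kg.** The stated 4.4% implies a one-infusion median of about 629, a ratio of 629/487 = 1.29. Applying that ratio to 631 to 706 gives an exceedance of 23% to 38% at 30 kg with both infusions.

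**8. No s.c. drug on board.** The base scenario of Table 7.5: 2 places 16 of 27 expected first flares on placebo. Without s.c. drug the second peak is 566 to 637, still above 487, and the exceedance is 1.8% to 4.9%.

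**The case against.** The strongest defence has four parts.

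- **The label concerns timing.** The worst-case wording is explained by placing the infusion at the s.c. peak. That is true as far as it goes, but the section then concludes on exposures under the doses planned, and those include the second infusion. This reading does not rescue the text.
- **The regimen stays within what was tested.** This stands. The two-infusion median peak is below 992 and the AUC is about half of 31,900. Giving the same modelled 40 kg patient 20 mg/kg weekly for four doses (800 mg × 4) yields a median peak of about 711 to 800 mg/L and a 12-week AUC of 22,800 to 25,500, above the two-infusion range. Section 4.1.2 also reports that weekly 20 mg/kg was tolerated and that exposure in GPP patients was lower than in healthy volunteers, so figures from a model built on healthy volunteers and PPP patients may run high. And 992,000 ug/L is an observed maximum, not a toxicity limit.
- **Few patients are affected.** This also stands. The 300 mg q4w arm expects about 2 first flares, the planned minimum is 8 adolescents, and at most about 2 in 7 rescued patients would qualify. Local laboratory checks before infusion, post-infusion monitoring and an external DMC are in place.
- **The choice of 40 kg is unchanged.** Agreed: the like-for-like comparison still favours 40 kg.

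These points limit how serious the gap is. None of them makes the stated margin apply to a patient given both infusions.

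**Conclusion.** The concern holds. Section 4.1.2 presents Cmax, AUC and exceedance for one infusion as the upper case, while the current protocol permits two, and nothing in the visible text covers two. That much follows from the documents alone.

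At 40 kg on q4w dosing, the exceedance given both infusions is probably several percent rather than 0.5%. The fitted range is at or above the 4.4% that the protocol cites against 30 kg, although that 4.4% is itself a one-infusion figure. The range rests on linear kinetics, the assumed distribution and absorption rates, and an unchanged spread; looser assumptions widen it to about 1% to 22%. The direction does not depend on these choices.

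No harm is shown, and no change of dose or weight limit follows from this. It should be corrected because the figure supports an eligibility threshold.

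**What to change.** Re-run the existing population PK model with 900 mg at R1/D1 and at R3/D8, at 40 kg and, for a like-for-like comparison, at 30 kg. Report Cmax, 12-week AUC and exceedance given both infusions and, if wanted, weighted for the chance of qualifying. Then amend Section 4.1.2 so that the worst case is the two-infusion one, the low-weight statement no longer refers to one i.v. dose only, and the R3/D8 criteria point to Table 3.1: 3.

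The cost is one model run at two weights and a text change. The stated margin will look less favourable, and the sponsor must say whether it is still acceptable at 40 kg. No endpoint, test or sample size is touched.

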4.1.3 Method of assigning patients to treatment groups

An Interactive Response Technology (IRT) will be used to screen eligible patients, perform drug assignment, manage initial/re-supply ordering of drug supplies and handle emergency un-blinding. The investigator will receive all necessary instructions to access the IRT from the Sponsor. Detailed IRT functions and procedures will be documented in the user requirement specifications mutually agreed to by the sponsor and the IRT vendor.

During Visit 2 and after the patient's eligibility is confirmed, patients will be randomized to blinded treatment arms according to a randomization plan in a 1:1:1:1 ratio. Randomization will be stratified by the stratification factor, concomitant use of systemic GPP medications at randomization (yes versus no) (see [Section 7.4](#)) and the blocking factors, region (Japan versus Non-Japan) and population (Adults versus Adolescents) (see [Section 7.4](#)). The assignment will occur in a blinded fashion via Interactive Response Technology (IRT).

At randomization as well as subsequent medication administration visits (including rescue treatment administration visit (s) with OL BI 655130 in the event that a patient experiences a GPP flare), IRT will assign medication numbers. Note that the medication number is different from the patient number (the latter is generated during screening via the IRT System). Each syringe and vial will have an individual medication number for dispensation.

4.1.4 Drug assignment and administration of doses for each patient

Prior to each administration of study drug, a urine pregnancy test will be performed on site. If this test has a positive result, the administration of study drug should not proceed and this urine test should be confirmed by a serum pregnancy test.

To maintain the treatment blind during the trial, all patients will receive 4 injections at Week 1/Day 1 for the loading dose followed by 2 injections at subsequent dosing visits in the every 4 weeks schedule.

Table 4.1.4: 1 Treatments used in this trial

Randomized Maintenance Treatment Period		
Arm	Loading Dose (Blinded) Week 1/Day 1	Maintenance Treatment (Blinded) Week 4 through Week 44
Arm 1: 300 mg BI 655130 q 4 weeks	4 x BI 655130 150 mg/PFS	2 x BI 655130 150 mg/PFS s.c. q4 weeks
Maintenance Treatment Period		
Arm	Loading Dose (Blinded) Week 1/Day 1	Maintenance Treatment (Blinded) Week 4 through Week 44
Arm 2: 300 mg BI 655130 q 12 weeks	4 x BI 655130 150 mg/PFS	2 x BI 655130 150 mg/PFS s.c. q12 weeks (i.e. at Week 12, Week 24, Week 36) 2 x Placebo to match Solution for Injection (BI 655130), 1mL PFS, at the intervening visits (i.e. at Week 4, Week 8, Week 16, Week 20, Week 28, Week 32, Week 40 and Week 44)

Table 4.1.4:1 (cont'd) Treatments used in this trial

Maintenance Treatment Period		
Arm	Loading Dose (Blinded) Week 1/Day 1	Maintenance Treatment (Blinded) Week 4 through Week 44
Arm 3: 150 mg BI 655130 q 12 weeks	2 x BI 655130 150 mg/PFS 2 x Placebo BI 655130 150mg/ml, 1mL PFS, 0mg/syringe	1 x BI 655130 150 mg/PFS 150 mg s.c. + 1 x Placebo to match Solution for Injection (BI 655130), 1mL PFS s.c. q12 weeks (i.e. at Week 12, Week 24, Week 36) 2 x Placebo to match Solution for Injection (BI 655130), 1mL PFS at the intervening visits (i.e. at Week 4, Week 8, Week 16, Week 20, Week 28, Week 32, Week 40 and Week 44)
Arm 4: Placebo	4 x Placebo BI 655130 150mg/ml, 1mL PFS, 0mg/syringe	2 x Placebo to match Solution for Injection (BI 655130), 1mL PFS s.c. q4 weeks
In case of a GPP Flare		
	Rescue Treatment (Open Label) at R1/Day 1 Or at R1/Day1 & R3/Day8	Maintenance Treatment (Open Label)
	2 x BI 655130 450 mg/vial (60 mg/mL)	2 x BI 655130 150 mg/PFS s.c. q12weeks Or 2 x BI 655130 150 mg/PFS s.c. q4weeks (intensified maintenance therapy)

During the randomized maintenance treatment period (Blinded) and maintenance treatment period (Open Label), the treatment will be administered subcutaneously. Injections during randomized maintenance treatment period will be given in a double blind fashion. Injections being given in the same area should be at least 2 cm apart and should not be close to a vein. The injection site should avoid sites where the skin is tender, bruised, erythematous, or indurated, and should be alternated to other areas for subsequent doses. Detailed instructions for administration of the s.c. injections are provided in the ISF.

OL 900 mg BI 655130 i.v. dose(s) will be used as GPP flare treatment, followed by a maintenance dosing schedule with OL 300 mg BI 655130 s.c. q12 weeks (and subsequently OL 300 mg BI 655130 s.c. q4 weeks, if needed). The infusion solution is intended to be

intravenously administered over a period of 90 minutes. In case of safety concerns, e.g. due to systemic hypersensitivity including infusion reactions, it is at the discretion of the investigator or his/her designee to adapt the infusion scheme, including but not limited to slowing down the infusion rate, stopping the infusion, and provided no further safety concern exists, restarting at a slower rate. Regardless, the total duration of infusion should not exceed 180 minutes (3 hours). Patients should be closely monitored for signs and symptoms of hypersensitivity reactions for 1 hour following the end of i.v. study drug administration. Hypersensitivity reactions should be treated according to medical standards. Further based on his/her medical judgment the investigator will provide medications as needed. Detailed instructions for the preparation of the i.v. infusion solution, the volume to be administered and the infusion rate are provided in the ISF.

Subcutaneous administration of biologic agents may involve the risk of local (injection site) or systemic hypersensitivity reactions. Therefore, patients should be closely monitored for signs and symptoms of injection site or systemic hypersensitivity reactions following study drug administration. Study personnel should observe the injection site for signs of redness, swelling or hardness. They should also ask subjects about itching, dizziness or shortness of breath. Patients should be advised that if they experience redness, swelling or other changes at the injection site, they should notify site personnel. They should further be advised that if they experience itching all over or a feeling of being swollen, dizzy or short of breath, they should notify site personnel or their own healthcare provider immediately. Pre-medications for further injections might be considered and will be agreed on between investigator and BI clinical monitor (see also [Section 6.2.2](#)).

The administration of the study medication will be done under supervision of the investigating physician or a designee at the site.

Dose modifications or adjustments are not permitted. In exceptional cases of missed or delayed visits, if any of these visits has to be rescheduled, the date of subsequent visit should be calculated from Day 1. In case of missed visits (during the randomized treatment trial period), the patients should be given the assigned medication for both visits (i.e. up to 1 missed visit and the current visit) at the next scheduled visit.

During the COVID-19 pandemic, physical visits to the sites may need to be restricted to ensure patient's safety. Based on a thorough assessment of the benefits and risks, the investigator may still decide to continue the trial treatment and the administration of the study medication may be performed at patient's home under the supervision of the investigating physician or a designee. The trial medication may be shipped to the patient's home if acceptable according to local law and regulations. This must be approved by the sponsor's trial team.

